	(3) Intervention : Four weekly, 1 hour 30 minute group mindfulness training sessions co-facilitated by an experienced mindfulness instructor (Faculty advisor [name]) and a clinical psychologist with pain psychology training (PI [name]).					
	(4) Post-measures: Within 1-2 weeks after intervention, administered via online self-report questionnaires and with semistructured phone interview.					
Efficacy Evaluations	Feasibility and acceptability will be measured with 1) enrollment statistics, 2) study retention, 3) assessment completion, 4) session attendance, 4) home practice diaries, and 5) credibility questionnaire and semi-structured phone interviews assessing participant satisfaction. Secondary outcomes will be measured with self-report questionnaires.					

Pharmacokinetic Evaluations	N/A
Safety Evaluations	Participant self-report of adverse experiences in response to mindfulness meditation practice. Will assess during intervention sessions. Will monitor AEs/SAEs that may or may not be study related as reported by participants.
Statistical And Analytic Plan	Primary feasibility/acceptability outcomes will be analyzed using percentages and 95% CIs. The qualitative description method will be used for interview data by identifying major themes within the content and producing a descriptive summary of the data. Secondary outcomes will be analyzed using paired t-tests and by examining the pre/post intervention change in scores and their respective standard errors with 95% confidence intervals.
Data And Safety Monitoring Plan	The PI ([name]) is responsible for data quality management and ongoing assessment of participant safety. The faculty advisor ([name]) will advise PI [name] on issues of data quality management and assessment of safety.

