2 STUDY OBJECTIVE

The objective of this study is to determine the feasibility and acceptability of a 4-week mindfulness program adapted from MBSR for adults with CNCP treated in UNC clinics.

2.1 Primary Objectives:

- 1: Determine the feasibility of recruiting via pain management providers and online advertisement, retaining participants, session attendance, and online data collection of quantitative measures during a 4-week mindfulness program for adults with CNCP 2: Determine participant acceptability and satisfaction with the intervention using quantitative measure of intervention credibility and with individual semi-structured interviews.
- **Secondary Objective:** Assess preliminary effects of the intervention on self-reported functioning, quality-of-life, depressive and anxiety symptoms, pain severity and interference, and other psychological variables that have been shown to improve with mindfulness training and may have beneficial impacts on chronic pain management.

3 INVESTIGATIONAL PLAN (brief overview)

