4.4 Follow- up procedures (by visits)

Post-Test Questionnaires: After the final intervention session (week 4), participants will be emailed a link with a REDCap survey containing all of the questionnaires from the

baseline survey, excluding demographic information. It will also include questions on intervention credibility.

Post-Test Interview: With-in 1 to 2 weeks after the final session, participants will be scheduled for a 15 to 30-minute semi-structured phone interview with the PI to assess participants' experience with the intervention sessions and overall study. Questions will address the following: satisfaction and usefulness of the skills and content, acceptability of the format, any challenges, and any suggestions for improvement of the intervention or study procedures.

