6.1 Primary Endpoint

The primary outcomes are feasibility and acceptability of the intervention and study procedures. Feasibility will be assessed as 1) ability to enroll 12 participants for one intervention group within 4-6 weeks, 2) participant retention, with a goal of 85% retention, 3) session attendance, with a goal of 75% sessions attended, 4) proportion of completed assessments and practice forms.

Acceptability will be assessed via credibility questionnaire and semi-structured interview assessing satisfaction with the intervention, barriers to engagement, and suggestions for improving the intervention or study procedures.

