6.3 Statistical Methods

Quantitative Analyses: Baseline demographic, pain medication use, and pain condition variables will be characterized using means and percentages and their standard deviations. Primary feasibility/acceptability outcomes will be analyzed using percentages (proportions) and 95% confidence intervals (CIs). Secondary outcomes will be analyzed by using paired t-tests and examining the pre/post intervention change in scores and their respective standard errors with 95% confidence intervals. Influence of the pretest score on change (i.e., ceiling and floor effects) will be investigated.

Qualitative Analyses: The qualitative description method will be used for interview data.²⁶ Major themes within the content will be identified and a codebook created. A test sample of interviews will be coded and the codebook refined, followed by coding remaining interviews. The outcome will be a descriptive summary of the contents of the data.

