APPENDIX A.
Schedule of Evaluations

Assessment	Phone Screening	Consent: Online form	Pre-test: Online Survey	Treatment Visit 1 (Week 1)	Treatment Visit 2 (Week 2)	Treatment Visit 3 (Week 3)	Treatment Visit 4 (Week 4)	Post-test: Online Survey	Post-test: Phone Interview
Inclusion/Exclusion Criteria	Х								
Informed Consent Review and Form	х	Х							
Feasibility: Enrollment, retention, attendance, data collection	х	Х	х	х	х	х	х	х	х
Acceptability: Satisfaction, barriers, suggestions to improve intervention								х	х
Demographics, pain conditions/regions			Х						
Instructor fidelity to intervention protocol				х	Х	х	Х		
Daily home practice and pain intensity/interference (exploratory outcomes)				х	X (daily from W1- 2)	X (daily from W2- 3)	X (daily from W3- 4)		
Pain medication usage			Х					Х	
Secondary outcomes: PROMIS outcomes, psychological variables			х					х	
Credibility Questionnaire					Х				
Adverse Reactions/Events				х	Х	Х	Х		

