Appendix B. Measures

Scale or Item	Description
Screening Measures/Items	
Drug Abuse Screening Test ²⁷ (DAST)-10	10 items; assess drug use in the past 12 months
Alcohol Use Disorders Identification Test	3 items; assesses alcohol consumption, drinking
(AUDIT) ^{28,29}	behaviors, and alcohol-related problems
Chronic pain	Have you experienced pain on a daily basis for at least
	3 months?
Pain bothersomeness	How bothersome was your pain in the previous week?
	(rating scale 0-10).
Pain interference with general activities	How much did your pain interfere with your general
	activities in the past week? (rating scale 0-10).
Diagnosis of mental illness with psychotic	Have you ever been diagnosed with schizophrenia,
features	schizoaffective disorder, or another psychiatric
	disorder with psychotic symptoms?
Psychiatric hospitalization in past 2 years	Have you ever been hospitalized for mental health
	reasons? When was the last hospitalization?
Previous mindfulness training	Have you ever participated in mindfulness training or
	course? Have you ever had a regular mindfulness
	practice? When?
Baseline-only Measures	
Demographic variables	Age, race/ethnicity, education, income, marital status
Pain conditions and regions	e.g. fibromyalgia, osteoarthritis, low-back pain,
	migraine, neck pain, etc
Baseline and Post-test Measures*	
Pain Medication Use	Pain medications taking, frequency, and dose
Physical Function (short-form 4a) ³⁰	4 items; difficulty with activities of daily living
Anxiety (sf 4a)	4 items; suggestive of anxiety in the past 7 days
Depression (sf 4a)	4 items; suggestive of depressed mood in past 7 days
Sleep Disturbance (sf 4a)	4 items; sleep quality and disturbance in past 7 days
Pain Interference (sf 6b)	6 items; degree to which pain interferes with life
Pain Intensity	1 item; average pain intensity past 7 days (0-10)
Positive Affect and Wellbeing	9 items;
Perceived Stress Scale – 4	4 items; global measure of perceived stress
Pain Catastrophizing Scale ³¹	13 items; 3 subscales characterizing thoughts and
	feelings when in pain – rumination, magnification,
	helplessness
Chronic Pain Acceptance Questionnaire ³²	20 items; acceptance of experiencing pain
Freiberg Mindfulness Inventory	14 items; measures all aspects of mindfulness
Intervention Satisfaction	1 likert-type item asking how satisfied are with the
2.22	intervention oveall
Credibility Questionnaire ^{34,35} (after session	5 items assessing opinions about the intervention

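### Section 6.3 reports acceptability as percentages, but the only quantitative measure named for it, a 5-item credibility questionnaire, has no response scale, scoring rule or cut-off

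*Combined protocol and SAP*

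**What the plan says.** Section 6.1 makes feasibility and acceptability the primary outcomes. On the second it says: "Acceptability will be assessed via credibility questionnaire and semi-structured interview assessing satisfaction with the intervention". The second primary objective in section 2.1 agrees ("using quantitative measure of intervention credibility and with individual semi-structured interviews"), and so does the Efficacy Evaluations row of the synopsis ("credibility questionnaire and semi-structured phone interviews assessing participant satisfaction").

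Section 6.3 gives the analysis: "Primary feasibility/acceptability outcomes will be analyzed using percentages (proportions) and 95% confidence intervals (CIs". The synopsis repeats this. Section 6.3 separately assigns the interview data to qualitative description, ending in a descriptive summary.

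The Measures appendix (Appendix B) describes the credibility questionnaire as "5 items assessing opinions about the intervention" and lists the topics: how logical it seems, confidence, recommending it, importance and success. It also lists an overall satisfaction measure, "1 likert-type item asking how satisfied are with the" intervention. The schedule in Appendix A has a row headed "Acceptability: Satisfaction, barriers, suggestions to improve intervention", marked at the post-test survey and the phone interview. Section 6.1 mentions satisfaction only as an interview topic.

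On timing, section 4.4 says of the post-test survey: "It will also include questions on intervention credibility". Appendix A marks the credibility questionnaire at week 2, and Appendix B places it after session 2.

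**The concern.** A percentage needs a numerator. For retention, attendance and completed forms the numerator is clear from the name of the outcome. For a set of opinion items it is not: someone must decide which answers, or which total, count as acceptable. The plan does not decide this, and its stated method invites the analyst to do so with the data in hand.

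Section 13 says that results on acceptability will be published and that the study will supply preliminary data for grant proposals. The other acceptability source is an interview conducted by the PI (section 4.4), who also co-instructs the sessions (sections 4.3 and 7). A quantitative summary fixed in advance is therefore worth having. Reducing about 20 scores to a yes/no count also discards information that a mean would keep.

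**Working it through.** **1. The plan's own figures (section 6.4).**

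- Retention: 1.96 × √(0.85 × 0.15 / 24) = 0.143, giving (0.71, 0.99). This matches the stated 0.14.
- Attendance: design effect 1 + (4 − 1) × 0.10 = 1.3, so 1.96 × √(0.75 × 0.25 × 1.3 / 96) = 0.099, giving (0.65, 0.85). This matches the stated 0.10.
- Post-test number: 24 × 0.85 = 20.4, stated as 20.

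All three reproduce. None concerns acceptability, for which section 6.4 gives no figure.

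**2. What the percentage in 6.3 could be applied to.**

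| Source | Named in 6.1 | Scale or categories given | Cut-off given | Goal given |
|---|---|---|---|---|
| Interview | yes | not applicable (qualitative) | no | no |
| Credibility, 5 items | yes | no | no | no |
| Satisfaction, 1 item | no | Likert-type, options not listed | no | no |

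For contrast, section 6.1 gives goals of 85% for retention and 75% for attendance.

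**3. Illustration for credibility.** The scale, mean, SD and normal shape are all assumptions. Take a mean item score on a 1-9 scale with mean 6.5, SD 1.5 and n = 20. The share at or above cut c is 1 − Φ((c − 6.5)/1.5), rounded to whole participants, with exact 95% CIs.

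| Cut | Model share | Count | Percentage (95% CI) |
|---|---|---|---|
| 5 | 0.841 | 17/20 | 85% (62-97%) |
| 6 | 0.631 | 13/20 | 65% (41-85%) |
| 7 | 0.369 | 7/20 | 35% (15-59%) |
| 8 | 0.159 | 3/20 | 15% (3-38%) |

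Moving the assumed mean between 6 and 7 gives 75-91% at a cut of 5 and 9-25% at a cut of 8. A different assumption, a 0-10 scale with mean 7 and SD 2, gives 84%, 69%, 50% and 31% at cuts of 5, 6, 7 and 8. The normal model is rough: it puts 1 − Φ((9 − 6.5)/1.5) = 5% above the top of the first scale and 1 − Φ((10 − 7)/2) = 7% above the top of the second.

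**4. The same scores on their own scale.** With mean 6.5, SD 1.5 and n = 20, the t-based half-width is 2.093 × 1.5/√20 = 0.70, giving a 95% CI of 5.8 to 7.2. No cut-off enters.

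**5. Illustration for the satisfaction item.** Assume five options with shares of 5, 5, 15, 40 and 35% and n = 20. Counting the top three options as satisfied gives 15 + 40 + 35 = 90% (68-99%). The top two give 75% (51-91%), and the top one gives 35% (15-59%). This item needs a stated cut-off as well.

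**6. Denominator.** If 20 of 24 respond at post-test and all 20 are satisfied, counting non-responders as not satisfied gives 20/24 = 83%. That ceiling reflects attrition only. The figure of 20 is a post-test number and need not apply to a questionnaire given after session 2.

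**The case against.** The strongest reply is that no threshold is needed. The documents do not say that the five items are summed. Reporting the percentage in each response category, item by item, would satisfy section 6.3 without any cut-off. That is correct, and it limits the point to any single acceptability percentage. It does not remove the point, because nothing in the plan commits to category-by-category reporting.

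The response scale may also sit in the instrument papers that the protocol cites, which were not available here. Even so, a published scale would not by itself supply a cut-off for acceptable, and the plan adopts none.

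It is also fair to say that this is a single-arm feasibility study with no hypothesis test on acceptability, and that the numbers above are assumed. Both stand. The illustrations show that a cut-off can matter, not how much it will matter in this trial.

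A reader might infer two stronger things that the documents do not support:

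- That acceptability cannot fail because it has no goal. The plan sets no pass/fail rule for any outcome: 85% and 75% are goals, and the proportion of completed assessments and practice forms has no goal either. The interviews ask about challenges and satisfaction and could show poor acceptability.
- That the satisfaction item would give a percentage without further definition. It is Likert-type, no response options are listed, and no category is called satisfied.

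**Conclusion.** The concern holds in a limited form. The plan commits a primary outcome to percentages, the only quantitative measure it names for that outcome has no scale, scoring rule or cut-off, and any single percentage from it would rest on a choice left open until after the data are seen. The body text and the appendices also disagree on when that measure is taken, so the time point and the likely number of respondents are unsettled.

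The size cannot be derived from the documents. Under the main assumed distribution the cut-off alone moves the figure from 85% to 15%, and under the alternative from 84% to 31%. That the cut-off is open does not depend on these assumptions. The retention and attendance analyses are unaffected. The change should be made because acceptability is a primary outcome and a better summary costs almost nothing.

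**What to change.** - **Section 6.3 and the synopsis:** take credibility out of the percentage sentence. Analyse it on its original scale, as mean (SD) with a t-based 95% CI, overall and by item. State the response scale and the scoring rule.
- **Section 4.4, Appendix A and Appendix B:** reconcile whether credibility is collected in the post-test survey, after session 2, or both, and say which time point the primary summary uses.
- **If a percentage is wanted:** name the existing overall satisfaction item in section 6.1, and in section 4.4, which does not list it in the post-test survey. List its response options and fix, before data collection, which of them count as satisfied. Report the full response distribution and the proportion with its 95% CI among responders, with the number responding out of 24. A version counting non-responders as not satisfied is at most a sensitivity analysis, because retention is already a separate primary outcome.

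The cost is wording. Both measures are already planned, so there is no new instrument and no added burden on participants. Naming the satisfaction item adds a quantitative acceptability measure to the two sources in section 6.1, so the second primary objective and the synopsis would need to match. The change has its full value only if made before the responses are seen.

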3.3 Study Duration, Enrollment and Number of Subjects

If recruitment proceeds as planned, the study from the beginning of enrollment to the last point of data collection could last approximately 6 months. However, up to one year will allocated should there be any issues with recruitment that need to be resolved or there is a need to wait to enroll between the first and second cohorts because of the time of year (e.g. holidays that would interfere with intervention sessions occurring for 4 consecutive weeks). One year is the allowable funding period. Participants will be enrolled on a rolling basis as they learn about the study, contact the study PI, and complete screening and consent procedures. We will attempt to limit each recruitment period to approximately 4 to 6 weeks to reduce the likelihood of attrition resulting from a prolonged waiting period between enrollment and the start of the group intervention. 12 participants will be enrolled in each group for a total of 24 participants.

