4.3 Intervention procedures (by visits)

The mindfulness intervention will consist of four, weekly group mindfulness skills sessions each lasting 1 hour and 30 minutes. Each session will allow time for a 5-minute break in the middle. Sessions will be co-instructed by PI [name] and faculty advisor [name]. All sessions will take place at the same location. See **Appendix B** for session-by-session content and home practice assignments. Participants will receive guided audio recordings for mindfulness skills practice, in addition to a binder with course handouts. The instructor will send one email to each participant the day after each session summarizing the session content and home practice assignments and encouraging participants to complete the daily mindfulness practice diaries. Sessions will be recorded to monitor fidelity to the intervention protocol. Participants will be asked to complete daily home practice and pain intensity diaries between session weeks 1 and 4 via online REDCap surveys that will be sent by email on a daily basis.

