6.4 Sample Size and Power

Anticipating a participant retention proportion of 0.85, the estimated half-width of a 95% CI for the proportion based on 24 enrolled participants is 0.14, which would give a CI of (0.71,0.99). Assuming the overall proportion of sessions attended is 0.75 and an intra-participant correlation of 0.10, the estimated half-width of a 95% CI for the proportion out of a total of 96 possible participant-sessions is 0.10, which would give a CI of (0.65,0.85). Assuming a 15% dropout rate, a sample size of 20 across two groups at post-test is adequate to estimate the feasibility and to generate preliminary data for planning a larger trial.

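### The paired analysis of secondary outcomes rests on the roughly 20 of 24 people who return both surveys, and no sensitivity analysis tests what the missing post-tests could do to the result

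*Combined protocol and SAP*

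**What the plan says.** Section 6.3 of the combined protocol and SAP analyses the secondary outcomes by "paired t-tests and examining the pre/post intervention change in scores", with standard errors and 95% CIs. It also plans to look at how the pretest score influences change. It defines no analysis set and gives no rule for a missing post-test.

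Section 6.4 expects missing post-tests: "Assuming a 15% dropout rate, a sample size of 20 across two groups at post-test" is described as adequate for estimating feasibility and for preliminary data to plan a larger trial. Section 3.3 gives the starting number: "12 participants will be enrolled in each group for a total of 24 participants". Section 4.8 foresees that some people will not return the post-test survey, but its rule is administrative: participation ends when the window closes. Section 13 intends to publish the preliminary effects and use them in grant proposals.

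On the diaries, section 4.3 says: "Participants will be asked to complete daily home practice and pain intensity diaries between session weeks 1 and 4". Appendix A lists daily pain among the exploratory outcomes. Section 6.1 counts the proportion of practice forms completed, but section 6 gives no analysis of the pain values.

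**The concern.** A paired analysis with no missing-data rule leaves out anyone without a post-test, together with any baseline score that person gave. The mean change then describes those who returned both surveys. It carries over to everyone enrolled only if the non-responders changed, on average, by the same amount.

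The protocol gives reasons why that may fail. Section 1.3 notes that training may at first increase distress, and section 4.8 withdraws anyone whose adverse event prevents completion of study procedures. It also gives a reason that need not relate to change: section 3.3 worries about loss during a long wait before the group starts. The plan contains no check that would tell these situations apart or show how much they matter.

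At stake is the preliminary change estimate that goes into a publication and into the planning of the next trial.

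**Working it through.** **Inputs.** Enrolled: 24 (section 3.3). Dropout 15% and 20 at post-test (section 6.4). Retention 0.85 with CI 0.71 to 0.99 (section 6.4). The changes assumed for non-responders, and the values of b and d in step 4, are not in the documents.

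**1. The plan's own figures.**
- Post-test number: 24 × 0.85 = 20.4, stated as 20. Expected loss: 24 × 0.15 = 3.6, or 4 in whole people.
- Retention half-width: 1.96 × √(0.85 × 0.15 / 24) = 0.143. The plan says "the estimated half-width of a 95% CI for the proportion based on 24 enrolled participants is 0.14". It reproduces.
- Lower retention limit: 0.71 × 24 = 17 people, so 7 lost.

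**2. Precision of the paired estimate.** The 95% CI half-width is t(0.975, n−1)/√n, in SDs of change.
- 24 pairs: 0.42
- 20 pairs: 0.47
- 17 pairs: 0.51

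**3. Possible distortion.** Let the observed mean change be m with n pairs, and let the 24 − n non-responders change by k × m on average. The all-enrolled mean is [n + (24 − n)k] × m / 24, so observed divided by all-enrolled is 24 / [n + (24 − n)k].

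| Assumed change in non-responders | 4 missing | 7 missing |
|---|---|---|
| Same (k = 1) | 24/24 = 1.0 | 24/24 = 1.0 |
| Half as much (k = 0.5) | 24/22 = 1.09 | 24/20.5 = 1.17 |
| None (k = 0) | 24/20 = 1.20 | 24/17 = 1.41 |
| Equal worsening (k = −1) | 24/16 = 1.5 | 24/10 = 2.4 |

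The ratio can also fall below 1. If non-responders improved one and a half times as much, 4 missing gives 24/26 = 0.92.

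**4. What a mixed model would change.** Using the non-responders' baselines shifts the estimated change by (b − 1) × (4/24) × d. Here b is the slope of post-test on baseline, and d is the baseline difference between non-responders and responders in baseline SDs. With d = 0.5 assumed:
- b = 0.4: 0.6 × (4/24) × 0.5 = 0.05 SD in size
- b = 0.6: 0.4 × (4/24) × 0.5 = 0.03 SD in size

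To compare this with the CI, take equal variances and correlation equal to b. The SD of change is then √[2(1 − b)] baseline SDs, which is 1.10 for b = 0.4 and 0.89 for b = 0.6. The half-width with 20 pairs is about 0.51 or 0.42 baseline SD respectively. The shift is about a tenth of the half-width or less.

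**The case against.** The strongest reply has three parts.

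**Proportion.** This is a single-arm feasibility study. Sections 5.1 and 6 say that it is not powered for efficacy or for changes in secondary outcomes. An uncontrolled pre/post change is not a treatment effect under any analysis. Attrition is not hidden either: retention and assessment completion are primary outcomes reported with CIs, and withdrawal reasons are recorded. All of this stands, and it limits the consequence. It does not settle whom the reported change describes, and sections 6.4 and 13 give that change a use beyond this study.

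**The mixed model does little.** This is also right. Step 4 shows a small shift. A likelihood-based model handles dropout that depends on observed scores, and it does not remove bias when people leave because of change that was never observed. Someone lost during the wait may have no baseline, since section 3.1 places it in the week before the start, and the model cannot include that person. The zero-change analysis is therefore needed beside it.

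**The diaries.** A reader might infer that daily pain ratings would fill the gap for everyone who drops out. The documents do not support that. Diaries start with the course, so they have no pre-course value and contain nothing from anyone lost before session 1. Section 4.8 does not say that they continue after withdrawal. They cover pain and home practice, and cannot recover function, anxiety, depression or the psychological scales. Nor is the diary ignored, because form completion is counted as feasibility. A missing analysis for an exploratory variable is, by itself, only missing detail.

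**Conclusion.** The point holds as a modest, cheaply mended gap. Under the plan's own dropout, about 4 of 24 people contribute to no secondary change estimate, and nothing planned shows how sensitive the result is to them. With 4 missing, the observed mean is 1.0 to 1.20 times the all-enrolled mean as non-responders range from equal change to no change. Worsening would take it higher, and better-than-average change would take it below 1. These ratios rest on assumed behaviour of non-responders and on the expected 20 pairs.

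Two stronger readings should be resisted. A reader might infer that the paired estimate flatters the programme; the documents give plausible routes to that, but also routes unrelated to outcome, so the direction is unknown. A reader might also infer that it describes programme completers. Section 4.4 does not make the post-test survey conditional on attendance, so the paired set is people who returned both surveys, and some of them may have missed sessions.

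The primary feasibility endpoints are unaffected.

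**What to change.** Add to section 6.3:

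1. Report each mean change and 95% CI from a linear mixed model with time as a fixed effect and an unstructured 2×2 covariance, fitted by REML to everyone with a baseline score. With complete data this gives the paired mean change.
2. Add one bounding analysis that sets change to zero for missing post-tests. Label it a reference scenario rather than a worst case, because worsening would lie beyond it.
3. Report the number of pairs for each outcome, and baseline scores by whether the post-test was returned.
4. Optionally, use the daily pain ratings as supportive data for people who leave after session 1, stating that they have no pre-course value and speak only to pain.

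This needs no new data and no change to procedures. The cost is a few sentences, a little analysis work and possibly a less favourable estimate.
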